11.13 Appendix 13. COVID-19 Guidance

- Subjects who test positive for coronavirus disease 2019 (COVID-19) using a test consistent with the institutional standard of care or who are exhibiting symptoms consistent with COVID-19 should not be enrolled in the study until complete resolution of symptoms.
- If an enrolled subject is exhibiting symptoms consistent with COVID-19, contact the Amgen Medical Monitor within 1 business day to ensure appropriate documentation and management of study activities.
- If a subject is unable to travel to the site for protocol-specified study visits and procedures, he/she can remain in the trial, provided that safety monitoring can occur. Alternatives, such as telemedicine to conduct visits, should be considered.
- On-site monitoring visits may be replaced by remote monitoring visits during COVID-19. Additionally, remote source document verification may be utilized for critical data points.
- Additional COVID-19 guidance from Food and Drug Administration (FDA) and European Medicines Agency (EMA) should be followed in consultation with Amgen medical monitor.

Amendment 4

Protocol Title: A Phase 1b Study Evaluating the Safety, Tolerability, Pharmacokinetics, and Efficacy of AMG 160 in Subjects with Non-Small Cell Lung Cancer

Amgen Protocol Number (AMG 160) 20180273

NCT Number: NCT04822298

Amendment Date: 25 March 2022

Rationale:

This protocol is being amended due to a change in the key safety risks for AMG 160. [REDACTED]

[REDACTED]

[REDACTED]

Amendment 3

Protocol Title: A Phase 1b Study Evaluating the Safety, Tolerability, Pharmacokinetics, and Efficacy of AMG 160 in Subjects with Non-Small Cell Lung Cancer

Amgen Protocol Number AMG 160 20180273

EudraCT number: to be determined

NCT Number: NCT04822298

Amendment Date: 19 October 2021

Rationale:

This protocol is being amended to address site shortages of tocilizumab. Applicable sections of the protocol are being modified to clarify the use of siltuximab in place of tocilizumab for the treatment of potential cytokine release syndrome (CRS) during a treatment-related adverse event. [REDACTED]

[REDACTED]. Additional language was included to update/clarify other items in the protocol. The following changes were incorporated into the study:

- Electrocardiograms (ECGs) were removed from the primary endpoints.
- [REDACTED]
[REDACTED]
[REDACTED]
- Added language to Overall Design in Sections 1.1 and 4.1 to allow additional subjects to be enrolled at 1 or more monotherapy dose levels that have been shown to be safe and tolerable.

- Subject Enrollment in Section 5.3 was modified to incorporate designee or staff members as additional personnel responsible for the documentation of subject enrollment to study.
- Added language to Subject Enrollment in Section 5.3 to clarify that:
 - subject enrollment in study will need additional confirmation from sponsor
 - study treatment should begin following study enrollment but no later than 7 days after enrollment
- Treatment/Other Protocol-Required Therapies Section 6.1.5 was added to clarify that sites are required to have tocilizumab or siltuximab for potential treatment of CRS.
- Criteria for use of siltuximab in place of tocilizumab, justification for the proposed dose and schedule, and safety stopping rules were included as Section 6.2.1.4.
- Added language to Concomitant Treatments Section 6.7.2 to clarify site availability of tocilizumab or siltuximab for CRS treatment.
- Added language to Section 8.1.1 to clarify that the use of standard of care radiographic assessments can be used for the screening process prior to signing of informed consent.
- Vital Sign Time Points Table 8-1 was updated to incorporate vital sign measurements for short term infusions.
- Added footnotes to Tables 6-3 and 11-7 to clarify the alternative use of siltuximab when tocilizumab is unavailable, and to incorporate a subgroup analysis that evaluates CRS outcomes, safety, and pharmacokinetic (PK) data of siltuximab-treated subjects.
- Administrative, typographical, and formatting changes throughout the protocol.

Amendment 2

[figure not shown]
Protocol Title: A Phase 1b Study Evaluating the Safety, Tolerability, Pharmacokinetics, and Efficacy of AMG 160 in Subjects with Non-Small Cell Lung Cancer

Amgen Protocol Number AMG 160 (acapatamab) 20180273

Amendment Date: 29 July 2021

Rationale:

The rationale for this protocol amendment is to include the following updates:

- Updated to include guidance relating to coronavirus disease 2019 (COVID-19):
 - Eligibility criteria was updated to exclude subjects that have severe acute respiratory syndrome coronavirus 2 (SARS-CoV-2) infection
 - Guidance for COVID-19 vaccinations was added (Sections 6.7.2 and 6.7.2.6)
 - Table 6-3 was updated to include management for subjects with asymptomatic and symptomatic SARS-COV-2 infection and COVID-19 disease

- Update to include minor clarifications regarding Statistical Considerations such as the modified toxicity probability interval (mTPI) (Section 9.2 and Table 11-3) and the futility analysis (Section 9.4.1.1)
- Several sections of the protocol have been updated to include required alignments with current Amgen protocol template (Sections 8.2.4, 8.2.4.1.3, 11.2, 11.3, 11.13).
- Administrative and editorial changes (including grammatical, typographical, and formatting) have been made throughout the protocol.

[figure not shown]
Superseded Amendment 1

Protocol Title: A Phase 1b Study Evaluating the Safety, Tolerability, Pharmacokinetics, and Efficacy of AMG 160 in Subjects with Non-Small Cell Lung Cancer

[figure not shown]
Amgen Protocol Number AMG 160 20180273

Amendment Date: 20 October 2020
Superseded Amendment Date: 25 January 2021

[figure not shown]
Rationale:

- Potential differences in prostate specific membrane antigen (PSMA) expression between castrate-resistant prostate cancer (CRPC) and non-small cell lung cancer (NSCLC) may lead to disease-related safety profile differences. Given the potential for a different safety profile in NSCLC, the starting dose has been adjusted to begin at 1 dose level below the RP2D identified in Study 20180101

- The dose limiting toxicity (DLT) definition has been modified to include additional life-threatening events, including Grade 4 anemia, Grade 4 non-hematologic laboratory abnormality of any duration and Grade 3 or higher thrombocytopenia with clinically significant bleeding regardless of duration of thrombocytopenia. Additionally, the DLT definition has been updated to include Grade 4 neutropenia lasting > 7 days, Grade 4 thrombocytopenia lasting > 7 days and Grade ≥ 3 transaminitis associated with CRS that resolves to grade ≤ 1 within 5 days. DLT criteria has also been updated to include AST/ALT/bilirubin elevations meeting Hy's law criteria as a DLT
- 

- Updated inclusion criteria # 105 regarding prior adjuvant or neoadjuvant chemotherapy to specify platinum-based adjuvant or neoadjuvant chemotherapy and to adjusted inclusion criteria # 105 to allow subjects who progress on at least 1 prior anti-PD1/PDL1 therapy and deemed unsuitable for treatment with chemotherapy or actively refused treatment with chemotherapy to be eligible
- 

On 25 January 2021, the protocol was superseded to correct minor typographical errors in the approved amendment.

[figure not shown]
Amendment 1

Protocol Title: A Phase 1b Study Evaluating the Safety, Tolerability, Pharmacokinetics, and Efficacy of AMG 160 in Subjects with Non-Small Cell Lung Cancer

[figure not shown]
Amgen Protocol Number AMG 160 20180273

Amendment Date: 20 October 2020

Rationale:

- Potential differences in prostate specific membrane antigen (PSMA) expression between castrate-resistant prostate cancer (CRPC) and non-small cell lung cancer (NSCLC) may lead to disease-related safety profile differences. Given the potential for a different safety profile in NSCLC, the starting dose has been adjusted to begin at 1 dose level below the RP2D identified in Study 20180101

- The dose limiting toxicity (DLT) definition has been modified to include additional life-threatening events, including Grade 4 anemia, Grade 4 non-hematologic

laboratory abnormality of any duration and Grade 3 or higher thrombocytopenia with clinically significant bleeding regardless of duration of thrombocytopenia. Additionally, the DLT definition has been updated to include Grade 4 neutropenia lasting > 7 days, Grade 4 thrombocytopenia lasting > 7 days and Grade ≥ 3 transaminitis associated with CRS that resolves to grade ≤ 1 within 5 days. DLT criteria has also been updated to include AST/ALT/bilirubin elevations meeting Hy's law criteria as a DLT

- Updated inclusion criteria # 105 regarding prior adjuvant or neoadjuvant chemotherapy to specify platinum-based adjuvant or neoadjuvant chemotherapy and to adjusted inclusion criteria # 105 to allow subjects who progress on at least 1 prior anti-PD1/PDL1 therapy and deemed unsuitable for treatment with chemotherapy or actively refused treatment with chemotherapy to be eligible

MTD	maximum tolerated dose
mTPI	modified toxicity probability interval
NSCLC	non-small cell lung cancer
ORR	objective response rate
OS	overall survival
PD	disease progression
PD1	programmed cell death protein 1
PDL1	programmed death-ligand 1
PET	positron emission tomography
PFS	progression-free survival
PK	pharmacokinetic(s)
PR	partial response

Abbreviation or Term	Definition/Explanation
PSMA	prostate-specific membrane antigen
RECIST	Response Evaluation Criteria in Solid Tumors
RP2D	recommended phase 2 dose
SAP	statistical analysis plan
SC	subcutaneous
SD	stable disease
t _{1/2}	half-life
TPI	toxicity probability intervals

1. Introduction

The purpose of this Statistical Analysis Plan (SAP) is to provide details of the statistical analyses that have been outlined within the protocol amendment 4 for study 20180273, AMG 160 dated 25 March 2022. The scope of this plan includes the interim analysis, the primary analysis and the final analysis that are planned and will be executed by the Amgen Global Biostatistical Science department unless otherwise specified.

2. Objectives, Endpoints and Hypotheses

2.1 Objectives and Endpoints/Estimands

Objectives	Endpoints

 Primary 	

 To evaluate the safety and tolerability of AMG 160 To evaluate the maximum tolerated dose (MTD) or the recommended phase 2 dose (RP2D) 	
 Dose-limiting toxicities (DLT) Treatment-emergent adverse events Treatment-related adverse events Changes in vital signs, electrocardiograms (ECGs), and clinical laboratory tests

 Secondary 	

 To characterize the pharmacokinetics (PK) of AMG 160 	
 PK parameters for AMG 160 following intravenous (IV) administration including but not limited to, maximum serum concentration (C_{max}), minimum serum concentration (C_{min}), area under the concentration-time curve (AUC) over the dosing interval, accumulation, and half-life (t_{1/2})

 To evaluate the preliminary anti-tumor activity of AMG 160 	
 Objective response (OR) per modified Response Evaluation Criteria in Solid Tumors (RECIST) 1.1 Overall Survival Progression-free survival (radiographic, clinical) Time to response Time to progression (radiographic, clinical) Duration of response Time to subsequent therapy

Exploratory

2.2 Hypotheses and/or Estimations

No formal statistical hypotheses will be tested.

3. Study Overview

3.1 Study Design

This is an open label phase 1b study evaluating the safety, tolerability, pharmacokinetics (PK), and efficacy of AMG 160 monotherapy in subjects with relapsed, refractory non-small cell lung cancer (NSCLC). There are 2 parts in the study,

- Dose-exploration
- Dose-expansion

Dose-exploration

The dose-exploration part of the study will estimate the MTD/RP2D of AMG 160 in NSCLC where the AMG 160 monotherapy will be administered as a short-term IV infusion every 2 weeks after target dose is reached in a 28-day cycle as monotherapy therapy. The starting dose of AMG 160 will be 1 dose level below the RP2D or otherwise the highest dose level deemed safe and tolerable as determined in the ongoing first in human (FIH) study of AMG 160 (Study 20180101) in subjects with mCRPC.

To mitigate the risk of CRS [REDACTED]

[REDACTED] Based on the MTD or RP2D and the associated dosing schedule

selected in Study 20180101, one of the following [REDACTED] schedules will be implemented: [REDACTED] infusion (see Table 6-1 in protocol for further details).

Dose Level Determination

Dose exploration will begin with 2 to 4 subjects. The study DLT window is 28 days. To be DLT evaluable, subjects must receive all planned cycle 1 doses of AMG 160. After a minimum of 2 subjects enrolled at a certain dose level are DLT evaluable, a DLRT meeting will be convened. Depending on observed safety data, the following may occur:

1. additional enrollment to dose Level 1; or
2. dose de-escalation to 1 dose below the starting dose; or
3. alternative dosing schedules, including further dose escalation, as per the ongoing mCRPC trial (Study 20180101), may be explored based on emerging safety and PK data.

Rules for dose-escalation/de-escalation are derived using a modified toxicity probability interval (mTPI) model with a target toxicity probability of 0.28.

Dose level decisions are made based on this posterior probability of toxicity, using 3 toxicity probability intervals (TPI):

- under-dosing TPI: DLT rate from 0 to < 23%
- target TPI: DLT rate from 23% to 33%, inclusive
- over-dosing: DLT rate > 33%

For the current dose level and after adjusting for the width of the under-dosing TPI, if the DLT rate is most likely in the under-dosing TPI then the recommendation is to dose escalate or stay at the current level. If the DLT rate is most likely in the target TPI then the recommendation is to stay at the current level. If the DLT rate is most likely in the over-dosing TPI then the recommendation is to de-escalate. If DLTs are observed, the MTD is the dose level with a DLT toxicity rate closest to 28%. The mTPI Trial monitoring table is described in [Table 3.1](#)

Table 3.1 . mTPI Trial Monitoring Table
Number of Subjects at current dose

# of DLTs	2	3	4	5	6	7	8	9	10
0	E	E	E	E	E	E	E	E	E
1	S	S	S	S	S	E	E	E	E
2	DU	D	S	S	S	S	S	S	S
3		DU	DU	D	D	S	S	S	S
4			DU	DU	DU	DU	D	S	S
5				DU	DU	DU	DU	DU	D
6					DU	DU	DU	DU	DU
7						DU	DU	DU	DU
8							DU	DU	DU
9								DU	DU
10									DU

[figure not shown]
E: Escalate to the next higher dose, if feasible; Otherwise, stay at the same dose;
 S: Stay at the same dose; D: De-escalate to the previous lower dose; DU: De-escalate to the previous lower dose and the current dose will never be used again in the trial

Dose Expansion

If 1 or more objective responses (OR) are observed (per modified RECIST 1.1 criteria) in dose exploration, additional subjects (up to 40) will be enrolled in dose expansion of the study at the MTD/RP2D identified in dose exploration. In dose expansion, 2 cohorts will be opened:

- Cohort 1 (up to 30 subjects with non-squamous NSCLC) and
- Cohort 2 (up to 10 subjects with squamous NSCLC).

Based on emerging safety and tolerability data in Cohort 2, the dose of AMG 160 could be lowered 1 dose level below the starting dose identified in dose exploration if necessary. Dose modification may occur as a result of interim analysis as described in [Section 7.1](#).

3.2 Sample Size

Up to 50 subjects will be enrolled in the study (approximately 10 subjects in a dose exploration phase and up to 40 subjects in a dose expansion phase). **Additional subjects (up to 20) may be enrolled in 1 or more monotherapy dose levels that**

have been shown to be safe and tolerable (defined as backfill enrollment). This backfill enrollment may be done to better estimate the RP2D and better characterize the safety, efficacy, PK, and [REDACTED] of AMG 160 monotherapy and may be concurrent with dose escalation to identify the MTD.

An initial 2 to 4 subjects will be enrolled and treated with Dose Level 1 (1 dose level below RP2D of AMG 160 Study 20180101). Rules for dose-escalation/de-escalation are derived using an mTPI model with a target toxicity probability of 0.28. If the dose is not tolerated (based on target DLT rate > 28%), the dose level will be reduced 1 level below the starting dose. Alternative dosing schedules, including further dose escalation as per the ongoing mCRPC trial (Study 20180101), may be explored based on emerging safety and PK data. The sample size in the dose exploration phase is based on practical consideration and is consistent with conventional oncology studies with the objective to estimate the MTD.

[figure not shown]
With 2 subjects in a cohort, there is a 19% to 55% probability of observing at least 1 DLT if the true DLT rate is 10% to 33% and with 4 subjects in a cohort, there is a 34% to 80% probability. With 6 subjects in a cohort, there is a 47% to 91% probability of observing at least 1 DLT if the true DLT rate is 10% to 33% and with 10 subjects in a cohort, there is a 65% to 98% probability.

In the dose expansion phase, a subject number of 40 will provide a 87% probability of observing at least 1 adverse event with 5% incidence rate. An exact 95% binomial CI will be provided for overall response rate. With the 40 subjects and 20% overall response rate, the expected 95% CI would be 9% to 36%.

4. Covariates and Subgroups

4.1 Planned Covariates

The relationship between covariates and efficacy endpoints may be explored if appropriate **and will be finalized in the Statistical Analysis plan before the database lock.**

5. Definitions

5.1 Study Endpoints

5.1.1 Primary Endpoints Definitions

Dose-limiting Toxicities (DLTs):

Investigators determine whether a TEAE qualifies as a DLT per the definition described in protocol section 6.2.1.3. For an adverse event to qualify as DLT, the start date must be within 28 days from the date of first dose of AMG 160.

Fridericia – corrected QT Interval (QTcF):

The Fridericia correction will be calculated from the investigator reported QT(msec) and RR interval (msec) as follows:

$$(QTcF=QT/(RR/1000)^{0.33})$$

Treatment-Emergent Adverse Event (TEAE):

Events categorized as Adverse Events (AEs) starting on or after first dose of investigational product (AMG 160) as determined by the flag indicating if the AE started prior to the first dose on the Events eCRF and including 30 days after the last dose of investigational product (AMG 160) or End of Study date or start of new anti-cancer therapy, whichever is earlier.

Treatment-Related Adverse Event (TRAE):

A treatment-related adverse event is any treatment-emergent adverse event that per investigator review has a reasonable possibility of being caused by the investigational product (AMG 160) determined by the flag indicating an event may have been caused by the investigational product (AMG 160) on the events eCRF. In the unlikely event that the flag is missing, the TEAE will be considered treatment-related.

5.1.2 Secondary Endpoints Definitions

Objective Response (OR) per RECIST 1.1:

Objective Response is defined as a best overall response ([Appendix C](#)) of either Complete Response (CR) or Partial Response (PR) per RECIST 1.1. Radiographic response (Complete Response, Partial Response) requires confirmation by a repeat, **evaluable** scan at least 28 days after the first documentation of response.

Subjects who do not experience a PR/CR or do not have any follow-up tumor assessments will be regarded as non-responders.

Overall Survival (OS):

Overall survival is defined as the time from the date of Study Day 1 until death due to any cause:

$$\text{OS time (Days)} = \text{date of death} - \text{Study Day 1} + 1.$$

Any subject not known to have died at the time of analysis will be censored based on the last recorded date on which the subject was alive.

Duration of Response (DOR):

The duration of response is defined as time from first evidence of CR or PR to disease progression or death due to any cause, whichever occurs first. DOR will be calculated only for subjects who achieve a best overall response of PR or CR.

$$\text{DOR (months)} = (\text{PD / death date} - \text{response start date} + 1) \times 12 / 365.25$$

The time of the initial response will be defined as the earliest of the dates contributing towards the first visit response of PR or CR.

- For confirmed responders whose PR or CR are confirmed in two **evaluable** assessments, the first PR/CR assessment among the two **evaluable** assessments will be used to calculate DOR.
- For unconfirmed responders awaiting follow-up confirmation scans, the PR or CR assessment that is awaiting confirmation scan will be used to calculate DOR.

Censoring rules for Duration of Response (DOR):

- Data for responders who are alive and without disease progression or new anti-cancer therapy are censored at the time of last **evaluable** tumor assessment **by CT/MRI scan**.
- Data for responders who are alive and without disease progression but who start new anti-cancer therapy are censored at the time of last **evaluable** tumor assessment **by CT/MRI scan** before the start of new anti-cancer therapy.
- Data for responders who die or have disease progression after two or more missed evaluable tumor assessments are censored at the time of last evaluable tumor assessments **by CT/MRI scan** before the two or more missed evaluable tumor assessments.

Details about the censoring rules are included in [Appendix E](#).

Radiographic Progression:

Disease progression per RECIST 1.1 occurs.

Radiographic Progression-free Survival (radiographic PFS):

Radiographic PFS is defined as the interval from Study Day 1 to the earlier of a radiographic progression or death from any cause; otherwise **PFS is censored based on criteria in [Appendix E](#)**.

Clinical Progression:

Clinical disease progression is based on clinical symptoms and are not associated with radiologic progression.

This is recorded by the field ‘disease progression is equal to clinical progression’ on the EOIP eCRF page.

Details about the censoring rules are included in [Appendix E](#).

Clinical Progression-free Survival (clinical PFS):

Clinical PFS is the time from Study Day 1 to clinical disease progression or death from any cause.

Details about the censoring rules are included in [Appendix E](#).

Time to Response (TTR):

TTR is defined as the time from the date of Study Day 1 to the date of the first documented CR or PR that is subsequently confirmed per RECIST1.1. For a subject who did not respond, time to response will be censored at the latest evaluable radiological assessment date. If a subject has no tumor evaluation in the study, time to response will be censored at the date of Study Day 1.

The time of the initial response will be defined as the earliest of the dates contributing towards the first visit response of PR or CR.

- For confirmed responders whose PR or CR are confirmed in two **evaluable** assessments, the first PR/CR assessment among the two **evaluable** assessments will be used to calculate TTR.
- For unconfirmed responders awaiting follow-up confirmation scans, the PR or CR assessment that is awaiting confirmation scan will be used to calculate TTR.

Time to Radiographic Progression:

Time to radiographic progression is defined as the interval from Study Day 1 to radiographic progression; otherwise, time to radiographic progression is censored based on the criteria in [Appendix E](#).

Time to Clinical Progression:

Time to clinical progression is defined as the interval from Study Day 1 to clinical progression; otherwise, time to clinical progression is based on the criteria in [Appendix E](#).

Subsequent Therapy:

Subsequent therapy is defined as subjects receiving anti-cancer therapies intended to treat NSCLC or any other anti-cancer therapies prior to end of study.

Time to Subsequent Therapy:

The time from Study Day 1 to the time a patient starts/receives the subsequent cancer therapy/subsequent therapy; otherwise time to subsequent therapy is censored at the last known date of any of the study assessment prior to initiating the subsequent cancer therapy/subsequent therapy.

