 - Subjects with a global deterioration of health status requiring discontinuation of treatment prior to radiologic confirmation of disease progression should have the reason for treatment discontinuation classified as 'clinical disease progression' not 'radiographic progressive disease'. Every effort should be made to radiologically confirm progression even after discontinuation of treatment.

Summary of Measurement and Tumor Response Assessment Based on Modified RECIST 1.1	
Measurable lesions	
 Non-nodal lesions: ≥ 10 mm (unidimensional measurement) Pathologic lymph nodes: longest diameter short axis ≥ 15 mm
Measurement of each lesion	
 Non-nodal lesions: The longest diameter (mm) in the axial plane Pathologic lymph nodes: short axis (mm)
Tumor burden	
 Sum of the longest diameters (SLD) of all target lesions Up to 5 lesions per organ, up to 10 total
Response assessment: target lesions (calculated from % change in tumor burden)	
 CR: Disappearance of all lesions 
 Pathologic lymph nodes short axis < 10 mm PR: $\geq 30\%$ decrease from baseline SD: Does not meet criteria for CR, PR or progressive disease. Progressive disease: $\geq 20\%$ increase (and ≥ 5 mm absolute increase) from nadir
Response assessment: non- target lesions	
 CR: Disappearance of all lesions 
 Pathologic lymph nodes short axis < 10 mm SD: Persistence of one or more non-target lesion(s) Progressive disease: Unequivocal progression of existing non-target lesions
New Lesions	The presence of new lesion(s) defines progression
Confirmation	Confirmation by subsequent assessment after ≥ 4 weeks required for CR, PR and progressive disease.

Summary of modified RECIST 1.1 Overall Response Assessment			
Target lesions (tumor burden) ^a , %	Non- target lesions	New lesions	Overall Response using modified RECIST 1.1
↓ 100%	Absent	Absent	CR ^b
None ^d	Absent	Absent	CR ^b
↓ 100%	Present	Absent	PR ^b
↓ $\geq 30\%$	Absent/Present	Absent	PR ^b
↓ $< 30\%$ to ↑ $< 20\%$	Absent/Present	Absent	SD
None ^d	Present	Absent	SD
↑ $\geq 20\%$	Any	Any	Progressive disease ^c
Any	Unequivocal progression	Any	Progressive disease ^c
Any	Any	Present	Progressive disease ^c
NA/ND/UE	Absent/Present	Absent	UE
None ^d	NA/ND/UE	Absent	UE

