Appendix E. Censoring Rules

Censoring rules for PFS or TTP (radiographic):

Situation up to DCO/EOS	Date of Event or Censoring	Outcome
No evaluable post-baseline or on-study disease assessment; On study without PD or death	Date of the first dose of investigational product (AMG 160)	Censored
PD prior to new anti-cancer therapy	Date of PD	Event
No PD, but death recorded without new anti-cancer therapy	PFS: Date of death; TTP: Date of last evaluable radiographic tumor assessment	PFS: Event; TTP: Censored
Start of new anti-cancer therapy prior to PD or death, or prior to any other disease assessment if there is no PD or death recorded	Date of last evaluable radiographic tumor assessment prior to the start of new anti-cancer therapy	Censored
No PD or death, no new anti-cancer therapy	Date of last evaluable radiographic tumor assessment	Censored
Death or PD immediately after more than one consecutively missed tumor assessment**	Date of last evaluable radiographic tumor assessment prior to the missing assessments*	Censored

DCO: data cutoff; EOS: end of study; PD: progressive disease

* This supersedes the previous rules that result in Event at date of PD or death

**Implementation details: censoring with death or PD immediately after more than one consecutively missed tumor assessment

Scenarios of PD or Death	Censoring Rule	X Days in Censoring Rule
While on treatment	If PD or death is X days after the last scan, censor at the last scan	119

Censoring rules for Duration Of Response (CT/MRI assessment):

Situation up to DCO/EOS	Date of Event or Censoring	Outcome
PD prior to new anti-cancer therapy	Date of PD	Event
No PD, but death recorded without new anti-cancer therapy	Date of death	Event
Start of new anti-cancer therapy prior to PD or death, or prior to any other disease assessment if there is no PD or death recorded	Date of last evaluable tumor assessment by CT/MRI prior to the start of new anti-cancer therapy	Censored
No PD or death, no new anti-cancer therapy	Date of last evaluable tumor assessment by CT/MRI	Censored
Death or PD immediately after more than one consecutively missed tumor assessment**	Date of last evaluable tumor assessment by CT/MRI prior to the missing assessments*	Censored

DCO: data cutoff; EOS: end of study; PD: progressive disease

* This supersedes the previous rules that result in Event at date of PD or death

**Implementation details: censoring with death or PD immediately after more than one consecutively missed tumor assessment

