Scenarios of PD or Death	Censoring Rule	X Days in Censoring Rule
While on treatment	If PD or death is X days after the last scan, censor at the last scan	119

Censoring rules for Clinical Progression-free Survival:

Situation up to DCO/EOS	Date of Event or Censoring	Outcome
No evaluable baseline or on-study disease assessment; on study without disease progression or death recorded.	Date of the first dose of investigational product (AMG 160)	Censored
Clinical progression	Date of clinical progression	Event
Death	Date of death	Event
All other scenarios	Date of last assessment	Censored

DCO: data cutoff; EOS: end of study;

Censoring rules for Time to Clinical Progression:

Situation up to DCO/EOS	Date of Event or Censoring	Outcome
No evaluable baseline or on-study disease assessment; on study without disease progression or death recorded.	Date of the first dose of investigational product (AMG 160)	Censored

Clinical progression	Date of clinical progression	Event;
All other scenarios	Date of last assessment	Censored

DCO: data cutoff; EOS: end of study;

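### Clinical PFS and time to clinical progression have no rule for radiographic progression or new anticancer therapy, so a subject who stops for scan progression has a clinical PFS event only at death

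*SAP*

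**What the plan says.** The protocol (Section 3) lists PFS and time to progression as secondary anti-tumor endpoints, each in a radiographic and a clinical version. SAP 5.1.2 defines the clinical versions:

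- Clinical progression: "Clinical disease progression is based on clinical symptoms and are not associated with radiologic progression".
- Data source: "This is recorded by the field ‘disease progression is equal to clinical progression’ on the EOIP eCRF page".
- Clinical PFS: "Clinical PFS is the time from Study Day 1 to clinical disease progression or death from any cause".
- Time to clinical progression: "Time to clinical progression is defined as the interval from Study Day 1 to clinical progression".

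In SAP Appendix E, the table headed "Censoring rules for Clinical Progression-free Survival" has four rows: no evaluable assessment and no progression or death (censored at first dose), clinical progression (event), death (event), and everything else (censored at "Date of last assessment"). The table for time to clinical progression is the same without the death row. The radiographic PFS/TTP table has a row that the clinical tables lack: "Start of new anti-cancer therapy prior to PD or death, or prior to any other disease assessment if there is no PD or death recorded", censored at the last evaluable scan before that therapy.

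SAP Table 9-1 plans Kaplan-Meier medians with 95% CIs for all of these endpoints.

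**The concern.** A reader will take clinical PFS to mean time alive without progression. Under these rules it mixes two quantities: time to symptomatic discontinuation for some subjects, and survival, including survival on later therapy, for those who stop because of a scan. Protocol Section 1.2 continues treatment until confirmed progression, so stopping for a scan is an expected route off treatment. Time to clinical progression has a different fault. Subjects who can no longer record the event remain in the risk set and are then censored as though their outlook matched that of subjects still on treatment. Two of the secondary endpoints for anti-tumor activity would then be hard to interpret, and clinical PFS would look better than the progression data support.

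**Working it through.** The documents give no median, event count or power for these endpoints, so there is no figure to reproduce. The main check is a trace of subject types through SAP 5.1.2 and Appendix E. It assumes that the EOIP field holds one type of progression, as its wording implies; the eCRF itself is not in the documents.

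**Rule trace**

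| Subject | Clinical PFS | Time to clinical progression |
|---|---|---|
| Stops for radiographic PD, death recorded | Event on death date, equal to OS, with or without later therapy | Censored at last assessment |
| Stops for radiographic PD, alive at cutoff | Censored at last assessment (undefined) | Censored at last assessment |
| Deteriorates and stops before radiologic confirmation | Event (clinical) | Event |
| Stops for toxicity, clinical progression later | No field named to record it; event only at death | Censored |

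**One subject (assumed history).** PD on the week 8 scan, confirmed 4 to 6 weeks later, treatment stopped for radiographic PD, new therapy, death at month 14.

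- Radiographic PFS dated at the first PD scan: 56 × 12 / 365.25 = 1.8 months. Dated at confirmation (day 84 to 98): 2.8 to 3.2 months.
- Clinical PFS: 14 months, event. OS: 14 months.
- Time to clinical progression: censored at the last assessment.

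**Illustrative size.** These inputs are assumed and are not in the documents: exponential times; median time to progression 2 to 4 months; median survival after progression 4 to 8 months; death without progression, median 24 months; 10%, 20% or 40% of progressions coded clinical; 0% or 15% off drug earlier for another reason; cutoff uniform at 12 to 24 months; 200,000 simulated subjects per setting. The composite is the earliest of either type of progression or death.

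Share of gap = (clinical PFS median − composite median) / (OS median − composite median).

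| Share coded clinical | Share of gap |
|---|---|
| 10% | 87–89% |
| 20% | 72–79% |
| 40% | 45–57% |

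Example: progression median 2 months, post-progression survival 6 months, 20% clinical, none off drug early. Composite 1.8, clinical PFS 6.4, OS 8.2 months, so (6.4 − 1.8) / (8.2 − 1.8) = 4.6 / 6.4 = 72%.

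- All settings: composite 1.8–3.4, clinical PFS 4.1–10.7, OS 6.4–11.6 months.
- If the last assessment means the last scan, the example gives 5.8 months, (5.8 − 1.8) / 6.4 = 63%, and the overall range is about 39–83%. The undefined term therefore changes the estimate.
- Limits in the example setting: 0% coded clinical gives clinical PFS = OS (8.2 months); 100% gives the composite (1.8 months).
- For time to clinical progression, with follow-up running to death or cutoff, the Kaplan-Meier median was not reached in any 10–40% setting.

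**The case against.** The split into clinical and radiographic versions is deliberate and comes from the protocol. Scan progression is reported beside the clinical endpoints, as radiographic PFS and TTP, by central and by investigator review (SAP 9.5.2). No hypothesis is tested (SAP 2.2), and no futility or safety rule uses these endpoints. Whether a symptom-based endpoint should absorb scan progression is partly a design preference. All of this stands. It limits what is at stake, but it does not make the clinical endpoints interpretable under their present names.

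A reader might infer that every subject with PD on a scan stays progression-free until death. The documents do not support that. Living subjects are censored. Protocol Appendix 12 (Section 11.12) also directs that "Subjects with a global deterioration of health status requiring discontinuation of treatment prior to radiologic confirmation of disease progression" be classed as clinical progression, and the confirming scan comes 4 to 6 weeks after the first, so some subjects with an initial PD scan do reach a clinical event.

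A reader might also infer that time to clinical progression drifts towards OS. It does not, because death is not an event there; its fault is informative censoring.

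The size is also open. In a second illustration (median progression 3 months, median OS 9 months, 8-weekly scans, all deaths observed), a clinical share of 10–30% gives medians of 6.9–8.3 months against 3.7 when either progression counts. A share of 50% gives 5.6 against 3.7, and 70% gives 4.3 against 3.5. The direction is stable, but a large excess is not established.

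**Conclusion.** The point holds as a fault in the definitions and censoring rules of two descriptive secondary endpoints. For a subject who stops for radiographic PD and later dies, equality of clinical PFS with OS follows from the text, given a single-valued EOIP field. So does the unconditional censoring in time to clinical progression. The direction of the drift is certain wherever some progressions are radiographic only. Its size is not known: every simulated figure rests on assumed event times and on an assumed share coded clinical, and should be read as illustrative.

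Two inconsistencies belong with it. The SAP separates clinical progression from radiologic progression, whereas Protocol Appendix 12 allows a clinical classification in a subject whose scan progression awaits confirmation. Protocol Table 1-6 recognises clinical progression during follow-up imaging after treatment ends, but the SAP names no source for it after the EOIP page.

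**What to change.** In SAP 5.1.2 and Appendix E, do one of the following.

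1. Define PFS for this purpose as the earliest of clinical progression, radiographic progression or death, with the new-anticancer-therapy censoring row already used for radiographic PFS. State whether the investigator or the central read supplies PD, and the PD confirmation convention. SAP Appendix C does not require confirmation for best overall response; Protocol Appendix 12 does require it.
2. Keep the clinical-only endpoint under a label that does not imply freedom from progression, and add the composite in (1) beside it. For time to clinical progression, treat radiographic PD, new therapy and death as competing events and report cumulative incidence.

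In either case, define the last assessment. Reconcile the SAP wording on clinical progression with Protocol Appendix 12 and Table 1-6, and name a data source for clinical progression after the EOIP page or state that it is not counted. Leave radiographic PFS and TTP as they are.

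Cost: SAP wording and some extra derivation, doubled if both reads are used. Radiographic PD, death and new-therapy dates are already needed for other endpoints; clinical progression after the EOIP page may need extra capture. The reported clinical PFS becomes less favourable.
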